92 ***glycemic control, as measured by change in HbA1c (non-inferiority limit of 0.4%),***  
93 ***compared to treatment with basal-bolus insulin regimen in patients with poorly***  
94 ***controlled T2D (HbA1c  $\geq$ 9-15%).***

- 95 - Primary outcome: change in HbA1c from baseline after 26 weeks of treatment with  
96 IDegLira vs basal-bolus insulin (with metformin, unless contraindicated).
- 97 - **Hypothesis:** After 26 weeks of treatment, IDegLira will result in similar improvement in  
98 glycemic control compared to basal-bolus insulin therapy.

99 **Specific Aim 2:**

100 ***2. To determine whether treatment with IDegLira will result in lower rate of***  
101 ***hypoglycemic events and less glycemic variability (superiority), as measured by***  
102 ***continuous glucose monitoring (CGM), compared to basal-bolus insulin in patients***  
103 ***with T2D and HbA1c  $\geq$ 9-15%.***

- 104 - Patients with poorly controlled T2D randomized to IDegLira or basal-bolus (with  
105 metformin, unless contraindicated) will have a one-week blinded CGM study performed  
106 during follow-up visits at 1, 12, and 26 weeks as well as 8-point self-monitored blood  
107 glucose (SMBG). CGM will allow better detection of hypoglycemic events, particularly  
108 asymptomatic and nocturnal hypoglycemia. It will also provide critical information on  
109 time in glycemic range and glycemic variability.
- 110 - **Hypothesis:** IDegLira will result in less hypoglycemia and glycemic variability  
111 compared to basal-bolus insulin regimen.

112 **Specific Aim 3:**

113 ***3. To determine whether treatment with IDegLira will result in improved patient***  
114 ***satisfaction compared to treatment with basal-bolus in patients with T2D and high***  
115 ***HbA1c ( $\geq$ 9-15%).***

- 116 - Patients with poorly controlled T2D randomized to IDegLira or Basal-Bolus will  
117 complete the Diabetes Treatment Satisfaction Questionnaire (DTSQ) and Treatment-  
118 related impact measures for diabetes (TRIM-D) survey during follow-up visits.
- 119 - **Hypothesis:** Use of IDegLira is associated with higher patient satisfaction and  
120 adherence compared to a multiple-daily injection regimen with basal-bolus insulin.

122 **CURRENT STATUS OF WORK IN THE FIELD**

123 **Epidemiology and treatment of patients with poorly controlled T2D and HbA1c >9%**

124

125

126       Based on NHANES data from 2007-2010, up to   135   with Diabetes: US and Emory Data

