271                   (responder’s rate)
- 272                   • Percent of patients reaching A1c  $< 7.5\%$  without weight gain and no hypoglycemia”
- 273                   • Percent of patients with A1c  $> 10\%$  and  $> 11\%$  that achieve A1c  $< 7.5\%$  and  $< 8\%$

- Percent of patients with HbA1c <7.0% at 26 weeks and no weight gain
- Percent of patients with HbA1c <7.0% at 12 weeks and no hypoglycemia
- Incidence of documented symptomatic hypoglycaemia, defined as an event with typical symptoms of hypoglycaemia accompanied by SMBG or CGM (<70 mg/dL and < 54 mg/dL) that occurs at any time of the day
- Incidence of asymptomatic hypoglycaemia, defined as no typical symptoms reported by the subject but detected by SMBG or CGM (<70 mg/dL and < 54 mg/dL)
- Incidence of severe hypoglycaemia, defined as severe cognitive impairment requiring assistance from another person
- Incidence of nocturnal symptomatic hypoglycaemia, defined as an event with typical symptoms of hypoglycaemia accompanied by SMBG or CGM <70 mg/dL and < 54 mg/dL that occurs between 00:00 and 05:59 hrs
- Incidence of nocturnal asymptomatic hypoglycaemia, defined as SMBG or CGM <70 mg/dL and < 54 mg/dl between 00:00 and 05:59 hrs
- Percentage of time below 70 mg/dL and <54 mg/dl as obtained by CGM
- Percentage of time in range (BG 70-180) as measured by CGM
- Glycemic variability, as measured by SD (standard deviation), %CV (coefficient of variance), Mean Amplitude Glucose Excursions (MAGE)
- Patient satisfaction and quality of life, as measured by the DTSQ and T R I M - D questionnaires
- Number of emergency room visits and hospital readmissions
- Change from baseline in total insulin dose (units/day)
- Number of treatment emergent AE

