580 • We will only analyze CGM data collected after the first 24 hours from insertion. Patients  
581 should have worn the CGM for at least  $> 4$  days.

582 • Documented symptomatic hypoglycemia, defined as an event with typical symptoms of

hypoglycemia confirmed by SMBG or CGM (< 70 mg/dL and < 54 mg/dL) that occurs at any time of the day

- Incidence of asymptomatic hypoglycemia, defined as no typical symptoms reported by the subject but detected by SMBG or CGM (<70 mg/dL and < 54 mg/dL)
- Incidence of severe hypoglycemia, defined as severe cognitive impairment requiring assistance from another person
- Incidence of nocturnal symptomatic hypoglycemia, defined as an event with typical symptoms of hypoglycemia confirmed by SMBG or CGM < 70 mg/dL and < 54 mg/dL that occurs between 00:00 and 05:59 hrs
- Incidence of nocturnal asymptomatic hypoglycemia, defined as no typical symptoms reported by the subject but detected by SMBG or CGM (<70 mg/dL and < 54 mg/dL) between 00:00 and 05:59 hrs
- Confirmed hypoglycaemia includes: severe hypoglycemia and episodes with or without symptoms with biochemical confirmation of glucose < 54 mg/dL.
- Relative hypoglycemia includes: typical symptoms but with glucose > 70 mg/dL

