**Assessments for Safety**

801 The safety endpoint of the study will be incidence of hypoglycaemia, as measured by the

802 current standard-of-care of POC monitoring. Subjects will complete an 8-point POC BG log  
803 before weeks -1, 12, 26. In addition, we will perform blinded/professional CGM studies for 7  
804 days, during week -1, 12, and 26. CGM will allow better detection of hypoglycemic events,  
805 particularly asymptomatic and nocturnal hypoglycemia, usually not detected by POC monitoring.  
806 It will also provide critical information on time in glycemic range and glycemic variability. We will  
807 also compare differences in glycemic variability, by SD, %CV and MAGE. GV will be calculated  
808 by mean daily standard deviation (SD) of glucose values in absolute terms, and as a percentage  
809 of variance from the overall mean (%CV). These are measures of dispersion of glucose values  
810 around a measure of central tendency, which represents the overall glucose excursion during  
811 the study. We will also analyze GV by mean amplitude of glycemic excursion (MAGE), which  
812 represents the average of all BG excursions (up or down), with a magnitude of > 1 standard  
813 deviation of all BG measures.

814

815 **Potential Risks to the Subjects:**

816 **Hypoglycemia.** It is possible that following the proposed protocol, subjects receiving IDegLira  
817 or Basal-bolus may develop hypoglycemia, as defined above.

818 **Gastrointestinal side effects**, including nausea and vomiting are more common in patients  
819 treated with liraglutide compared to placebo. The frequency of nausea and vomiting is reported  
820 in up to 5-15% patients receiving IDegLira. The number of adverse events will be collected at  
821 each telephone contact or clinic visit. There have been few reported events of acute  
822 pancreatitis. Subjects should be informed of the characteristic symptoms of acute pancreatitis:  
823 persistent, severe abdominal pain. If pancreatitis is suspected, Degludec-liraglutide should be  
824 discontinued. If the investigator suspects acute pancreatitis, all suspected drugs should be  
825 discontinued until confirmatory test have been conducted and appropriate treatment should be  
826 initiated. Subjects diagnosed with acute pancreatitis (as a minimum 2 of 3: characteristic  
827 abdominal pain, amylase and/or lipase >3xUNR or characteristic findings on CT scan/ MRI  

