### 866 **Subject Compliance**

867 Subject compliance will be assessed by monitoring of drug accountability. Subjects will be  
868 encouraged at every visit to adhere to the study medications and follow-up schedule. Unused  
869 trial medications will be compared with dispensed amount at each corresponding visit. If  
870 discrepancies are noted, the subject will be asked.

871  
872 **STATISTICAL CONSIDERATIONS:**  
873 **Sample Size Calculation**  
874       The primary outcome is the change in HbA1c from baseline after 26-weeks of treatment.  
875       The primary hypothesis is that HbA1c change is similar between the IDegLira group and the  
876       basal-bolus group. Given the data reported for the DUAL V study, we assume the HbA1c  
877       change from baseline has a standard deviation bounded above by 0.85 (%). We assume the  
878       margin of equivalence is 0.4 (%) and the true mean difference in the primary outcome is 0 (%).  
879       Given 57 subjects per study group, based on a one-sided, two-sample t-tests, we would achieve  
880       80% power to detect non-inferiority, with alpha (type-1 error) set as 0.05. Accounting for 20%  
881       attrition rate of 20%, we need to recruit 75 subjects per group (150 in total).  
882  
883 **Statistical Methods**  
884       This is a randomized, open-label study. We will first compare the primary outcome (i. e.  
885       change in HbA1c from baseline to after 26 weeks of treatment) between the two study groups  
886       using nonparametric and parametric two-sample tests, such as Wilcoxon tests and t-tests. A  
887       logarithm transformation may be employed to make the data better conform to the normality  
888       assumption. We will apply standard variable selection and model checking procedures to decide  
889       the final model.  
890       Secondary outcomes include various measurements (related to glycemic control, quality  
891       of life, adverse effects, and etc.) collected at a single or multiple time points. For continuous  
892       outcomes measured a single time point (i.e. non-longitudinal outcome), we shall analyze them  
893       following the same strategy designed for the primary outcome. For discrete non-longitudinal  
894       outcome, we will use Chi-square (or Fisher's Exact) tests to compare them between the two  
895       study groups. This will be followed by logistic regression or Poisson (or Negative Binomial)  

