896       regression to assess other potential confounders. We will perform appropriate model selection  
897       and diagnostic procedures to ensure adequate fit to the data. For outcomes measured at  
898       multiple time points (i.e. longitudinal outcome), we will first conduct cross-sectional analyses as  
899       planned for the non-longitudinal outcomes. Next we will perform repeated measures analyses  
900       that account for with-subject correlations in the longitudinal outcomes. We will analyze  
901       longitudinal continuous outcomes based on repeated measures ANOVA followed by repeated  
902       measures linear regression, and we will analyze longitudinal discrete outcomes by using  
903       repeated measures generalized linear model (GLM). If the assumption of missing completely at  
904       random (MCAR) is reasonable, we shall handle missing data by excluding them from the cross-

905 sectional and the longitudinal data analyses. When MCAR assumption is questionable, we will  
906 assume missing values are missing at random and deal with them by the standard multiple  
907 imputation methods. We plan to conduct statistical analyses using SAS 9.4.

908

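### Aim 2 is about an event rate, but the named arm comparison ignores time at risk and no count model has a stated exposure term

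*Combined protocol and SAP*

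**What the plan says.** Specific Aim 2 is a superiority aim: "To determine whether treatment with IDegLira will result in lower rate of" hypoglycaemic events, measured by CGM. The matching secondary outcomes under Endpoints are worded as incidences, for example "Incidence of documented symptomatic hypoglycaemia, defined as an event with typical symptoms of hypoglycaemia accompanied by SMBG or CGM", and no denominator is given (patients, patient-time or sensor-time). A separate endpoint, "Percentage of time below 70 mg/dL and <54 mg/dl as obtained by CGM", is a proportion of wear time. Assessments for Safety also makes the incidence of hypoglycaemia by point-of-care monitoring the safety endpoint.

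For discrete outcomes at a single time point, Statistical Methods reads "outcome, we will use Chi-square (or Fisher's Exact) tests to compare them between the two" groups. It continues: "study groups. This will be followed by logistic regression or Poisson (or Negative Binomial") "regression to assess other potential confounders. We will perform appropriate model selection". Longitudinal discrete outcomes get the same cross-sectional tests first and then a repeated measures GLM. Missing data are excluded if MCAR is reasonable and otherwise multiply imputed under MAR.

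On exposure, Sample Size Calculation allows for 20% attrition, and Subject Replacement rules out replacing withdrawn subjects. Under Definitions, CGM data from the first 24 hours are discarded and patients "should have worn the CGM for at least" more than 4 days. The CGM visits section plans 7 days of wear. No section mentions an offset, patient-time, sensor-time or events per patient-year.

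**The concern.** A rate needs a denominator in time. A chi-square test on whether a patient had any event gives everyone the same denominator, however long they were observed, and ignores repeat events. A patient who leaves at week 4 has had less opportunity for an event than one who completes 26 weeks. A sensor with 3 usable days has less opportunity than one with 6. If such shortfalls fall more heavily on one arm, that arm looks safer with no true difference. The regression that could correct this is given another purpose and has no stated exposure term. At stake is whether a difference reported under Aim 2 reflects the drug or the amount of observation.

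**Working it through.** **The plan's own figure.** There is no sample size or power for Aim 2. The only such figure is for the primary outcome: 57 per arm, SD 0.85, margin 0.4, true difference 0, one-sided alpha 0.05. The noncentrality is 0.4/(0.85 × √(2/57)) = 2.51, and exact t power is 80.3%, so the stated 80% reproduces. 57/0.8 = 71.25, rounded up to 72; the planned 75 is slightly generous. This has no bearing on Aim 2 beyond fixing 75 per arm.

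**Inputs from the documents.** 75 per arm; 26 weeks; 20% attrition overall; 7-day sensor; first 24 hours dropped; wear above 4 days; 44% of patients with glucose below 70 mg/dL in the group's earlier discharge cohort (Current Status of Work in the Field).

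**Assumptions.** The 44% refers to 12 weeks. The event rate is constant and equal in both arms. Between-patient variation is gamma with dispersion k = 0, 1 or 2. Dropout is unrelated to events, and dropouts are kept and scored on what was observed. The dropout splits and timing are also assumed.

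**Step 1: sensor time.** The maximum is 7 − 1 = 6 days. The minimum is just over 4 − 1 = 3 days, if the 4 days count from insertion. Between two patients, exposure can differ almost two-fold.

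**Step 2: chance of any event by week t.** This is 1 − exp(−λt) for k = 0 and 1 − (1 + kλt)^(−1/k) otherwise. For k = 0, λ = −ln(0.56)/12 = 0.0483 per week. The chance is then 71.5% by week 26, 17.6% by week 4, and 43.1% on average for dropout spread evenly over 26 weeks. At 30% v 10% dropout, all at week 4, observed incidence is 0.7 × 71.5 + 0.3 × 17.6 = 55.3% against 0.9 × 71.5 + 0.1 × 17.6 = 66.1%.

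**Step 3: rejection by the nominal two-sided 5% chi-square with equal true rates** (range over k = 0, 1, 2; the same if the arms are swapped):

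| Dropout by arm | Spread over 26 weeks | All at week 4 |
|---|---|---|
| 20% v 20% | 4.9–5.6% | 5.4–5.6% |
| 25% v 15% | 6.2–6.5% | 7.7–11.0% |
| 30% v 10% | 7.8–11.3% | 14.3–28.4% |

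**Step 4: a count model without an offset.** Its rate ratio tends to the ratio of mean follow-up. At 30% v 10%, spread dropout gives (1 − 0.3/2)/(1 − 0.1/2) = 0.85/0.95 = 0.89. Week-4 dropout gives (0.7 + 0.3 × 4/26)/(0.9 + 0.1 × 4/26) = 0.746/0.915 = 0.82. Simulation (1,500 trials per scenario, k = 1 or 2, dispersion fixed at its true value, robust standard errors) gave median ratios of 0.90 and 0.81–0.82. Rejection rates were 8–10% (spread) and 14–16% (week 4).

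**Step 5: the same model with log follow-up time as offset.** It rejected 5.4–6.5% of the time in all twelve scenarios tried, up to 40% v 0% dropout. The Monte Carlo standard error is about 0.6 points.

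**The case against.** Several points on the other side are fair.

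- A reader might infer that chi-square is the whole plan. It is not: a count regression and a repeated measures GLM follow. Hypoglycaemia is recorded at each contact from week 1 to week 26, so it can be read as longitudinal. This stands, but neither model has a stated exposure term, the cross-sectional tests come first, and Step 4 shows that a count model without an offset does not remove the problem.
- The missing-data rule may take dropouts out of the comparison. Under the assumptions above, an analysis of completers shows no false difference. This also stands. The inflation in Step 3 arises only if partly observed patients are kept and scored on observed time, and the plan does not say how they are handled.
- Aim 2 is measured by CGM in fixed windows, so a patient who has left before a session has missing data, not shortened time. The 26-week calculation therefore bears on SMBG and symptomatic events. For CGM events the relevant exposure is wear within a session.
- A reader might infer that the bias favours IDegLira, because Potential Risks says nausea and vomiting are more common in patients "treated with liraglutide compared to placebo. The frequency of nausea and vomiting is reported" in up to 5–15% on IDegLira. That is a frequency of symptoms, not of withdrawal. The Background expects poorer adherence on basal-bolus, and the design rationale links extra injections to withdrawal. The documents support neither direction.
- A reader might treat unequal sensor days as a difference between arms. Both arms share the device, schedule and wear rule, and variation that is balanced across arms creates no false difference.
- Percent time below 70 and 54 mg/dL is already scaled to wear time and is not affected.

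**Conclusion.** The point holds as a gap in specification for a secondary aim. The question is a rate, the named arm comparison is a yes/no test, and no stated model takes account of time at risk. With equal dropout the chi-square keeps its level at about 5%. With imbalance it rejects 6–11% of the time at 25% v 15% and 8–28% at 30% v 10%, and the upper ends need all dropout to be early. A negative binomial model without an offset is affected to a similar degree at 30% v 10% (8–16%).

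These figures are scenarios, not forecasts. They rest on the assumed splits, timing, dispersion and 12-week horizon, and on scoring dropouts on observed time. The plan gives only 20% attrition overall, and nothing on dropout or wear by arm. It therefore supports saying that bias is possible in either direction. It does not support saying that a false advantage for IDegLira is expected. The primary HbA1c analysis is not touched.

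**What to change.** For the hypoglycaemia event endpoints, name one main arm comparison in Statistical Methods: a negative binomial model for the number of events, with arm, the HbA1c randomisation stratum (<10 v ≥10, from Randomization and Blinding) and log time at risk as offset. Time at risk is treatment time for SMBG and symptomatic events, and valid sensor time after randomisation for CGM events. Report the rate ratio with its 95% CI. Allow no data-driven covariate selection in this model. Keep chi-square or Fisher on any event as descriptive.

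State that patients who leave early contribute their events and their observed time. If the repeated measures GLM is kept for event counts, give it the same offset per period. The offset corrects for unequal time. It does not correct for dropout caused by hypoglycaemia or for a rate that changes during titration, so events and exposure should also be tabulated by arm.

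The cost is SAP wording. Visits are dated, and the minimum-wear rule already requires sensor time to be known.

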746           • HbA1c, Fasting Glucose/CMP and pregnancy test (WOCP per PI discretion) will be  
747            obtained

748           • CGM will be inserted

749           • Patients will complete the DTSQ and TRIM-D questionnaires

750           • AE and hypoglycemia data will be collected, as well as concomitant medications.

751           • Drug dispensing

752

753           **CGM visits (insertion on weeks -2, 12, 26 and collection on week 0, 14, 27)**

755           All enrolled participants will have a blinded/professional CGM study performed during  
756           week -2, 12, and 26 weeks of follow-up.

757           During this visit, participants will receive training on CGM use and reinforce SMBG diary  
758           collection. Trained personnel will proceed with sensor insertion, transmitter placement and  
759           hook-up. After that, the transmitter will be activated, the CGM session will be started.

760           After 7 days, subjects will remove the sensor and return to the scheduled visit. Transmitter  
761           will be connected to the computer for data downloading. CGM summary will be reviewed to  
762           determine the quality.

763           Sensor will be stored following standard precautions. Onsite visits will be allowed for upload of  
764           the study devices and face-to-face discussion about hypoglycemia and hyperglycemia

765 episodes, insulin doses, AE/SAE evaluation, and replacement of study medication, if required.  
766 Trained personnel will input required clinical and demographic data into the sensor database  
767 software. Subjects will complete an 8-point SMBG for 1 day (as shown in Table 1) prior to clinic  
768 visit. Subjects will bring their glucose meter, CGM sensor (if applicable), BG diary, to each  
769 onsite visit.

770 **Visit 17 (Week 26, end-of-study)**

- 771 • Diabetes Treatment Satisfaction Questionnaire Status (DTSQs) and TRIM-D survey
- 772 • Blood sampling as indicated on page 12- schedule of events during the study period,  
773 including HbA1c assessment to determine efficacy of treatment
- 774 • Study diaries collected and reviewed for BG levels, episodes of hypoglycemia, insulin  
775 self-administration

776

777 **Visit 18 (week 27, case sign-off)**

- 778 • This visit should occur at least one week after the last treatment visit
- 779 • Since degludec has a prolonged duration of action, this visit will serve to monitor for  
780 adverse events.

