### 851 **Other Assessments**

852 We will assess patient satisfaction by using the DTSQs at baseline and the DTSQc at the end-  
853 of-study, as recommended by Health Psychology Research.

854 For treatment satisfaction, subjects' responses to questions 1, 7 and 8 of the DTSQc will be  
855 used. A comparison of the score on the DTSQs from week 0 to week 24, as well as using the  
856 score on the other questions of the DTSQc, which would overcome the ceiling limitation of using  
857 the DTSQs by itself. The Diabetes Treatment Satisfaction Questionnaire Status (DTSQs) form  
858 will be administered at weeks 0, 12 and the DTSQc will be administered at week 26. The  
859 amplitude of the score on the DTSQc gives the degree of change in satisfaction, while the  
860 direction (positive or negative) will provide guidance on the preference of one treatment regimen  
861 over the other one.

862 For quality of life, we will use the "Treatment-related impact measures for diabetes" (TRIM-D)"  
863 in order to determine the impact of the type of therapy on this outcome. Subjects will be given  
864 the questionnaire at baseline, and weeks 12 and 26 to assess their quality of life and any  
865 potential impact of the treatment regimen .

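### The analysis of multi-visit continuous secondary outcomes fixes neither the pre-treatment reading as a covariate nor the deciding arm contrast, and this gives up precision that costs nothing to keep

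*Combined protocol and SAP*

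**What the plan says.** The protocol's Statistical Methods section treats outcomes with several readings in three steps.

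- **Cross-sectional tests.** For outcomes at "multiple time points (i.e. longitudinal outcome), we will first conduct cross-sectional analyses as" planned for single-time outcomes. Continuous single-time outcomes are handled "following the same strategy designed for the primary outcome. For discrete non-longitudinal" outcomes go to chi-square or Fisher tests. The primary strategy compares "change in HbA1c from baseline to after 26 weeks of treatment) between the two study groups" by Wilcoxon and t-tests, and then settles a final model: "assumption. We will apply standard variable selection and model checking procedures to decide" that model.
- **Repeated-measures ANOVA.** The plan analyses "longitudinal continuous outcomes based on repeated measures ANOVA followed by repeated"
- **Repeated-measures regression.** That sentence continues "measures linear regression, and we will analyze longitudinal discrete outcomes by using" a repeated-measures GLM. The terms of the linear regression are not listed.

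Pre-treatment readings exist. The CGM section is headed "CGM visits (insertion on weeks -2, 12, 26 and collection on week 0, 14, 27", and the Screening Visit text places the first sensor before drug exposure. For TRIM-D, Other Assessments gives "the questionnaire at baseline, and weeks 12 and 26 to assess their quality of life and any" treatment impact. Randomization and Blinding bases randomisation on HbA1c below 10 or at least 10.

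The plan does not say whether the pre-treatment reading is a response level, a covariate or the base of a change score. It also does not say whether the arm main effect, the arm-by-visit interaction or a single-visit difference decides.

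**The concern.** Aim 2 is a superiority aim, and its CGM variability measures depend on this paragraph. So does the TRIM-D part of Aim 3. The only sample size in the document is for HbA1c non-inferiority, so power for these outcomes is whatever the analysis delivers.

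Two things are at stake. First, leaving out the pre-treatment value, or using it only as the base of a change score, discards precision from a measurement already scheduled. Second, with several tests and no named contrast, a null result may reflect the choice of test, and a positive one may be picked from several. Bringing baseline in through data-driven variable selection would not be pre-specification.

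**Working it through.** **The plan's own figure.** SD 0.85, margin 0.4, true difference 0, one-sided 0.05, 57 per group. The noncentrality is 0.4 / (0.85 × √(2/57)) = 2.51, and the noncentral t with 112 df gives 80.3% power, so the stated 80% reproduces. With 75 recruited per arm and 20% attrition, 75 × 0.8 = 60 remain; I use 60 per arm below.

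**Assumptions (the documents give none of these).** Unit SD, equal correlation ρ between all visits, no arm difference before treatment, a true effect D = 0.5 SD at weeks 12 and 26, two-sided 0.05, normal theory. I show ρ = 0.3, 0.5 and 0.7.

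**Week 26 alone.** Each option estimates D. The variance per patient is 1 for raw values, 2(1−ρ) for change scores and 1−ρ² with baseline adjustment. The noncentrality is D / √(variance × 2/60).

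| Week-26 test | ρ = 0.3 | ρ = 0.5 | ρ = 0.7 |
|---|---|---|---|
| Raw | 78% | 78% | 78% |
| Change score | 63% | 78% | 94% |
| Baseline-adjusted | 81% | 88% | 97% |

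Against the adjusted analysis, the raw test needs 1/(1−ρ²) = 1.10, 1.33 and 1.96 times the patients. The change score needs 2(1−ρ)/(1−ρ²) = 2/(1+ρ) = 1.54, 1.33 and 1.18 times.

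**Three visits as responses, arm main effect tested.** The expected difference is (0 + D + D)/3 = 2D/3, with variance (1+2ρ)/3. Power is 70, 60 and 53%. The fair comparator is the unadjusted mean of weeks 12 and 26 (effect D, variance (1+ρ)/2), with 92, 88 and 84%. The loss is one third of the post-treatment mean effect whatever the week-12 effect is. Against the week-26 effect it is 33% if week 12 shows the same effect, 42% if three quarters of it and 50% if half. A simulation at 57 per arm (4,000 trials for each ρ) gave a mean estimate of 0.331 to 0.333 for D = 0.5, against 0.333 expected.

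**Arm-by-visit test.** It does not average the effect with baseline, but spends 2 df. With noncentrality (60/2)(2D²/3)/(1−ρ) on 2 and 236 df, power is 66, 81 and 96%.

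**Mean of weeks 12 and 26, adjusted for baseline.** Variance (1+ρ)/2 − ρ²; power 95, 97 and 99%. Averaging alone already gives 92, 88 and 84%, so only the rest (3, 9 and 15 points) comes from baseline.

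**Which outcomes fit three visits.** CGM and TRIM-D do. For SMBG, the Screening Visit text gives weeks 0, 12 and 26, but Table 1 also collects a profile at week 4. With four visits the main effect would be 3D/4, a loss of one quarter. DTSQ does not fit: Other Assessments gives the status form at weeks 0 and 12 and the change form at week 26.

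**The case against.** The strongest reply is that the plan already names repeated-measures linear regression, which can be exactly the model recommended here, and that its cross-sectional step inherits a strategy built on change from baseline. On that view this is missing detail and not a wrong method. Part of this stands. A reader might infer that the plan dilutes the arm effect by a third, or that baseline is wasted. The documents support neither. The dilution needs two choices that are not stated: baseline as a response level, and the arm main effect as the test. It does not touch tests at week 12 or 26, or an arm-by-visit test.

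The reply does not remove the point. Among the secondary endpoints only insulin dose is listed as a change from baseline, so whether change scores carry over to CGM and TRIM-D is unclear. Even if they do, the adjusted test is stronger at each ρ shown. An unspecified regression reached through variable selection does not secure the adjustment.

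Three further limits are fair. A reader might quote 97% against 78% as the value of baseline, but that comparison also moves from week 26 to an average over visits, which changes the estimand; the Rationale for study design justifies 26 weeks as the time to stable HbA1c. A reader might also infer that a null Aim 2 would be the method's doing, but the first outcome named in that aim is a rate of hypoglycaemic events, which falls under the discrete-outcome methods. Lastly, normal-theory power is not shown to apply to time below range, which is likely to be skewed.

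**Conclusion.** The point holds as a gap in specification with a measurable cost. For CGM, TRIM-D and SMBG means, the plan neither fixes the pre-treatment reading as a covariate nor names the deciding contrast. At week 26, adjustment is worth 3 to 19 power points over raw values (81−78 to 97−78) and 3 to 18 over change scores (97−94 to 81−63) for ρ from 0.3 to 0.7. This assumes 60 per arm, a 0.5 SD effect and equal correlations. The one-third shrinkage is conditional: it applies only to three-visit outcomes, and only if baseline is a response level and the arm main effect is tested. These are secondary outcomes, so the change is well worth making but does not threaten the primary analysis.

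**What to change.** Specify the repeated-measures regression already planned as the deciding analysis for the CGM, TRIM-D and SMBG measures:

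- responses: post-treatment visits only;
- fixed terms: arm, visit, arm-by-visit, the pre-treatment value of the same measure, and the HbA1c randomisation stratum (below 10, at least 10), with no variable selection on these;
- within-patient correlation modelled;
- one named arm contrast: either week 26, matching the primary time point, or the average of weeks 12 and 26.

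Treat the unadjusted cross-sectional tests and the repeated-measures ANOVA as descriptive. Choose one method for skewed time below range in advance.

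Reconcile the schedules on which the model depends. The first CGM is at week 1 in Specific Aim 2, week −1 in Assessments for Safety and week −2 in the CGM section. SMBG at week 4 appears in Table 1 but not in the Screening Visit text. Analyse the DTSQ status and change forms separately: Visit 17 lists the status form at week 26, while Other Assessments gives the change form then and also mentions a status comparison to week 24.

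The cost is wording only. The baseline readings are already scheduled, and no visit or patient is added.
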